8.3.4 TIME PERIOD AND FREQUENCY FOR EVENT ASSESSMENT AND FOLLOW-UP

The occurrence of an adverse event (AE) or serious adverse event (SAE) may come to the attention of study personnel during study visits and interviews of a study subject presenting for medical care, or upon review by a study monitor.

All AEs, including local and systemic reactions not meeting the criteria for SAEs, will be captured on the appropriate case report form (CRF). Information to be collected includes event description, time of onset, clinician's assessment of severity, relationship to study product (assessed only by those with the training and authority to make a diagnosis), and time of resolution/stabilization of the event. All AEs occurring while on study must be documented appropriately regardless of relationship. All AEs will be followed to adequate resolution.

Any medical condition that is present at the time that the subject is screened will be considered as baseline and not reported as an AE. However, if the study subject's condition deteriorates at any time during the study, it will be recorded as an AE.

Further details can be found in the Study Safety Plan.

8.3.5 ADVERSE EVENT REPORTING

The investigator must record non-serious adverse events and report them to the Sponsor in a timely manner after the investigator first learns of the adverse event. AEs which are non-serious not related to the research procedures does not have to be reported to the IRB but will be reviewed by the Sponsor and the Independent Medical Monitor.

In case however that the event is unexpected **AND** more likely than not related to the research procedures it shall be reported to the IRB within 5 days of Investigator receiving notice of the event, as per IRB local guidelines.

8.3.6 SERIOUS ADVERSE EVENT REPORTING

The study investigator shall report an Unanticipated Adverse Device Effect to the study sponsor and to the reviewing Institutional Review Board (IRB) as soon as possible, but in no event later than 5 working days (as per IRB local guidelines) after the investigator first learns of the effect. The study sponsor is responsible for conducting an evaluation of an unanticipated adverse device effect and shall report the results of such evaluation to the Food and Drug Administration (FDA) within 10 working days after the sponsor first receives notice of the effect. Thereafter, the sponsor shall submit such additional reports concerning the effect as FDA requests.

The sponsor must immediately conduct an evaluation of any unanticipated adverse device effect. If the sponsor determines that an unanticipated adverse device effect presents an unreasonable risk to subjects, the sponsor must terminate all investigations or parts of the investigations presenting that risk as soon as possible. Termination must occur no later than 5 working days after the sponsor makes this determination and no later than 15 working days after the sponsor first received notice of the effect.

Resumption of Terminated Studies:

For a nonsignificant risk device investigation, a sponsor may not resume a terminated investigation without IRB approval. If the nonsignificant risk study was terminated for unanticipated adverse device effects, the sponsor must also obtain FDA approval.

8.4 UNANTICIPATED PROBLEMS

8.4.1 DEFINITION OF UNANTICIPATED PROBLEMS (UP)

Unanticipated problems are defined as problems involving risks to subjects or others to include, in general, any incident, experience, or outcome that meets all of the following criteria:

- Unexpected in terms of nature, severity, or frequency given (a) the research procedures that are described in the clinical investigation plan-related documents, such as the approved research Clinical Investigation Plan and informed consent document; and (b) the characteristics of the subject population being studied;
- Related or possibly related to participation in the research ("possibly related" means there is a reasonable possibility that the incident, experience, or outcome may have been caused by the procedures involved in the research); and
- Suggests that the research places subjects or others at a greater risk of harm (including physical, psychological, economic, or social harm) than was previously known or recognized.

This definition could include an unanticipated adverse device effect, any serious adverse effect (USADE) on health or safety or any life-threatening problem or death caused by, or associated with, a device, if that effect, problem, or death was not previously identified in nature, severity, or degree of incidence in the investigational plan or application (including a supplementary plan or application), or any other unanticipated serious problem associated with a device that relates to the rights, safety, or welfare of subjects (21 CFR 812.3(s)).

8.4.2 UNANTICIPATED PROBLEM REPORTING

An investigator shall submit to the sponsor and to the reviewing Institutional Review Board (IRB) a report of any unanticipated adverse device effect occurring during an investigation as soon as possible, but in no event later than 10 working days after the investigator first learns of the effect (21 CFR 812.150(a)(1)). A sponsor who conducts an evaluation of an unanticipated adverse device effect under 812.46(b) shall report the results of such evaluation to the Food and Drug Administration (FDA) and to all reviewing IRB's and participating investigators within 10 working days after the sponsor first receives notice of the effect. Thereafter the sponsor shall submit such additional reports concerning the effect as FDA requests (21 CFR 812.150(b)(1)).

8.4.3 REPORTING UNANTICIPATED PROBLEMS TO SUBJECTS

In case an unanticipated problem would concern other study subjects they will be contacted by the study investigator.

9 STATISTICAL CONSIDERATIONS

9.1 STATISTICAL HYPOTHESES

9.1.1 PRIMARY

The primary purpose of the *SF* Study is to validate the effectiveness of the *Vibe Air SF* strategy based on the intended use and technological characteristics.

Please refer to Section 3 for more detail about the hypotheses. There are 3 APHAB communication subscales that contribute to the perceived benefit (response condition), and each subscale benefit (EC, BN, RV) must simultaneously demonstrate the non-inferiority of *Vibe SF* strategy to HCP fit strategy. Note that higher means are worse.

- H_0 EC(benefit): $\Delta EC(benefit)_{HCP \text{ fit}} - \Delta EC(benefit)_{SF} \geq 26$ vs
 H_a EC(benefit): $\Delta EC(benefit)_{HCP \text{ fit}} - \Delta EC(benefit)_{SF} < 26$
- H_0 BN(benefit): $\Delta BN(benefit)_{HCP \text{ fit}} - \Delta BN(benefit)_{SF} \geq 27$ vs
 H_a BN(benefit): $\Delta BN(benefit)_{HCP \text{ fit}} - \Delta BN(benefit)_{SF} < 27$
- H_0 RV(benefit): $\Delta RV(benefit)_{HCP \text{ fit}} - \Delta RV(benefit)_{SF} \geq 28$ vs
 H_a RV(benefit): $\Delta RV(benefit)_{HCP \text{ fit}} - \Delta RV(benefit)_{SF} < 28$

These are non-inferiority tests comparing the subject's perceived hearing aid benefit as measured by the difference in each of the three APHAB communication benefit subscales when the hearing aid is HCP fit compared to when it is *Vibe SF* by the subject. The non-inferiority margin (NIM) depends on the communication benefit subscale, according to Cox (1995), and these are the minimum clinically important differences on each of the three communication benefit subscales.

9.1.2 SECONDARY

The secondary objectives do not include any hypothesis tests. However, they will not be analyzed unless the primary effectiveness hypothesis test passes (i.e., rejects all 3 null hypotheses).

Descriptive statistics will be reported on each endpoint by fitting strategy and overall, according to the list in Section 9.4.1.1. In addition, some endpoints require more detailed description. Additional descriptive statistics that will be reported are listed with the endpoints.

EMA Scores: Descriptive statistics of the scores will be reported by fitting strategy and measurement time for each real-life condition.

QuickSIN Scores: Descriptive statistics of the scores will be reported by fitting strategy and measurement time.

SSQ-12 Scores: Descriptive statistics of the scores will be reported by fitting strategy and measurement time for each subscale.

Gain Selection: Descriptive statistics of the probe-mic REM will be reported by fitting strategy and measurement time.

Fitting Preference: Descriptive statistics of the scores will be reported by fitting strategy and measurement time.

Safety Analyses: It is very unlikely that any device-related adverse events will be reported during this NSR device study. However, those that are reported will be tabulated by severity (mild-moderate-severe), seriousness (serious or non-serious) and relatedness (related, not related).

9.2 SAMPLE SIZE DETERMINATION

The sample size was estimated for the Primary Effectiveness Objective; that is the only objective with a hypothesis test. The sample size of 24 was estimated using Pass 2019 and the following parameters:

Parameter	Value
Difference between HCP fit and Vibe SF scores (δ) 
 • EC(benefit) • BN(benefit) • RV(benefit) 	
 • $\delta = \Delta EC(benefit)_{HCP\ fit fit} - \Delta EC(benefit)_{SF} = 0$ • $\delta = \Delta BN(benefit)_{HCP\ fit fit} - \Delta BN(benefit)_{SF} = 0$ • $\delta = \Delta RV(benefit)_{HCP\ fit fit} - \Delta RV(benefit)_{SF} = 0$
SD (σ) of scores within a fitting strategy and for the difference between Vibe SF and HCP fit, assuming independence ($\sqrt{2\sigma^2}$)* 
 • EC(benefit) • BN(benefit) • RV(benefit) 	
 • $\sigma = 24.3; \sigma_{DIFF} = 34.4$ • $\sigma = 25.6; \sigma_{DIFF} = 36.1$ • $\sigma = 25.5; \sigma_{DIFF} = 36.2$ 
(Leohler & et al, 2017)

Non-inferiority margins (NIMs) 
 • EC(benefit) • BN(benefit) • RV(benefit) 	
 • EC(benefit) = 26 • BN(benefit) = 27 • RV(benefit) = 28 
(Cox & Alexander, 1995)

Power	90% on all 3 tests simultaneously, or 96.5% on each individually ($.965^3 = .90$)
Alpha	5% on all 3 tests simultaneously
Test Type	Paired t-Tests for Non-Inferiority

* The variance of the difference of two means is used, not 4 means, even though this is the difference of differences. The reason is that the baseline value (unaided) from which benefit is measured is the same for the SF period and the HCP fit period. Therefore, the difference of differences reduces to the difference between the aided SF score and aided HCP fit score.

** All 3 tests must simultaneously have $p < .05$

The sample sizes were estimated for each test at 80% and 90% power, as shown in the table below. The NIMs were chosen because each listening condition will be analyzed independently in order to determine if there are significant differences in each specific listening conditions. The largest sample size required for combined 90% power was 23. We will increase this to 24 so that the cross-over periods are balanced. A sufficient number of subjects will be included to allow for a minimum of 24 subjects (anticipate up to 15% drop out rate, 24+4) to successfully complete the study. If the parallel-arm design is used, we will increase this to 25 per arm (50 total subjects); for more details on this, please refer to the section on Planned Interim Analyses: 9.4.6.

These sample size tables are applicable to both the parallel-group design and the cross-over (paired or repeated-measures) design. This is because we had no information with which to estimate the *correlation* among pairs of measures, so we used 0 correlation. This is the same as independent treatment groups, or parallel-arm design. Using the largest sample size of the 3 tests, a cross-over design requires 23 subjects with endpoints and a parallel-arm design requires 23 subjects in each arm. Because we prefer that each order in a cross-over design have the same number of subjects, we increased it to 24. (Then the sample sizes were inflated for losses to follow-up, withdrawals, etc.)

Paired or Unpaired T-Tests for Non-Inferiority								
Numeric Results								
Higher Means are Worse								
EC Hypotheses: $H_0: \delta \geq NIM$ vs. $H_1: \delta < NIM$								
				Mean				
			Non-Inferiority	of Paired	Standard			
Power on Tests			Margin	Differences	Deviation			
Combined	Individual	N	NIM	$\delta 1$	σ	Alpha	Beta	
80%	0.93601	19	26	0	34.4	0.05	0.06399	
90%	0.96892	23	26	0	34.4	0.05	0.03108	
RV Hypotheses: $H_0: \delta \geq NIM$ vs. $H_1: \delta < NIM$								
				Mean				
			Non-Inferiority	of Paired	Standard			
Power on Tests			Margin	Differences	Deviation			
Combined	Individual	N	NIM	$\delta 1$	σ	Alpha	Beta	
80%	0.93457	18	28	0	36.1	0.05	0.06543	
90%	0.96942	22	28	0	36.1	0.05	0.03058	
BN Hypotheses: $H_0: \delta \geq NIM$ vs. $H_1: \delta < NIM$								
				Mean				
			Non-Inferiority	of Paired	Standard			
Power on Tests			Margin	Differences	Deviation			
Combined	Individual	N	NIM	$\delta 1$	σ	Alpha	Beta	
80%	0.93063	19	27	0	36.2	0.05	0.06937	
90%	0.96555	23	27	0	36.2	0.05	0.03445	

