Figure (c) shows an effect of treatment and order, and also an interaction effect. The interaction effect occurs because the difference between treatments is *not* the same with both orders. Compare this to Figure (b), in which the difference *is* the same. In this case, the test for non-inferiority of SF to HCP fit

Protocol #: D00232675

08 September 2021

must be done on SF First and HCP fit First separately because non-inferiority might be true in one case and not in the other.

It is important to note that it is not the order effect, but the interaction effect, that makes it impossible to do a non-inferiority test. The interaction term will be tested by combining the p-values from the 3 scales. The method WHM, shown in Section 9.4.2.1, will be used here, but in this case, it will be the interaction term p-values that are combined. The combined p-value will be compared to $\alpha=0.10$; if the null hypothesis of no interaction is rejected in favor of the hypothesis of an interaction, we will switch to the parallel-arm design.

If the design is switched to parallel-arm, then subjects who have not crossed over will have only one treatment, and subjects who have crossed over will have only their first treatment used in the analysis of the parallel-arm data. See Section 9.4.2.3.

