9.4.2.3 ANALYSIS OF PARALLEL-ARM DESIGN DATA

Each communication benefit subscale will be analyzed using a t-test of the benefit with SF (as described previously, the difference between baseline and SF score) versus the benefit with HCP fit (the difference between baseline and HCP fit score). ***The p-values for all 3 communication subscales must be 0.05 or smaller in order for the global hypothesis test to pass (reject the global null of inferiority).***

Because Sponsor would like to report a global p-value for these tests, the 3 p-values will be combined into a single value using the method of WHM as described as in Section 9.4.2.1. The p-values cannot be assumed to be independent because the data are from the same set of subjects, and it is therefore likely that the benefit on the EC score is correlated with the benefit on the RV score, etc.

Descriptive statistics for the treatment groups for each of the three communication benefit subscales, EC(benefit), RV(benefit), BN(benefit), at each time point will also be reported.

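### The 90% power for the parallel-arm branch is unsupported: Section 9.2 does not say which SD sigma is, and the unaided baseline does not cancel between different subjects

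*Combined protocol and SAP*

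**What the plan says.** The parameter table in Section 9.2 gives sigma as 24.3 (EC), 25.6 (BN) and 25.5 (RV). It describes sigma as the SD "of scores within a fitting strategy and for the difference between" the two strategies, on rows labelled as benefit. The SD of the difference is the square root of 2 times sigma squared. The footnote explains why two variances are used and not four: "the baseline value (unaided) from which benefit is measured is the same for the SF period and the HCP fit period", so "the difference of differences reduces to the difference between the aided SF score and aided HCP fit score".

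Below the table, Section 9.2 carries the result over to the other design: "These sample size tables are applicable to both the parallel-group design and the cross-over (paired or repeated-measures) design". The reason given is that no information on the correlation between paired measures was available, so zero was used: "This is the same as independent treatment groups, or parallel-arm design". Hence "a parallel-arm design requires 23 subjects in each arm", raised to 25 for drop-out (50 in total).

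Section 9.4.2.2 sets the trigger. If the null hypothesis of no interaction is rejected "in favor of the hypothesis of an interaction, we will switch to the parallel-arm design". Section 9.4.2.3 then gives the test: "Each communication benefit subscale will be analyzed using a t-test of the benefit with SF", against the benefit with HCP fit, each being baseline minus aided score. It names no baseline covariate.

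**The concern.** Zero correlation between a subject's SF and HCP fit scores makes a paired comparison of aided scores behave like a comparison of independent groups. It does nothing about the unaided scores. In the cross-over, the same unaided score is subtracted from both periods and drops out. In the parallel branch, each arm has its own subjects and its own unaided scores. Both sets stay in the contrast, because the test is on benefit.

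Whether this matters depends on what sigma measures. The row labels point to the SD of benefit. The footnote points to the SD of a single aided score, since its argument for two variances is needed only on that reading. No section settles it.

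At stake is the chance that the trial switches design, enrols up to 50 subjects, and fails to show non-inferiority of a device that is non-inferior. After a switch, this t-test is the primary analysis.

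**Working it through.** **Inputs from Section 9.2.** One-sided alpha 0.05 per test, true difference 0, margins 26/27/28 and sigma 24.3/25.6/25.5 (EC/BN/RV). Joint power is the product of the three powers, as in the plan (0.965 cubed = 0.90). **Assumptions, not in the documents:** the unaided SD equals sigma when sigma is read as an aided-score SD, and rho, the unaided-aided correlation, is shown over a range.

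**1. The plan's own figures.** Paired t-test, noncentral t with n − 1 df and noncentrality margin/(SD of difference/√n). For BN with n = 23: 27/(36.2/√23) = 3.58, power 0.96555. EC at n = 23 gives 0.96892 and RV at n = 22 gives 0.96942. All match the tables. (The parameter table interchanges the BN and RV SDs of the difference; the power tables have them right, since 25.6√2 = 36.2 and 25.5√2 = 36.1.)

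**2. Parallel t-test, sigma read as the SD of benefit.** Noncentral t with 2n − 2 df and noncentrality margin/(SD × √(2/n)). At 23 per arm the powers are 0.973/0.970/0.978, and the product is 0.923. At 25 per arm the product is 0.947. There is no shortfall.

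**3. Parallel t-test, sigma read as an aided-score SD.** SD of benefit = sigma × √(2(1 − rho)). At rho = 0 this is 34.4/36.2/36.1, and the powers at 23 per arm are 0.811/0.801/0.828.

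| rho | joint power, 23 per arm | joint power, 25 per arm |
|---|---|---|
| 0 | 0.54 | 0.60 |
| 0.3 | 0.77 | 0.82 |
| 0.4 | 0.85 | 0.89 |
| 0.5 | 0.92 | 0.95 |

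Joint power reaches 90% at rho of about 0.46 with 23 per arm and 0.42 with 25. If the unaided SD is 0.8 or 1.2 times sigma, the 23-per-arm figure becomes 0.36 or 0.57.

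The low end does not depend on the product rule. Joint power cannot exceed the weakest single test. That test is BN at 80% when rho = 0 with 23 per arm, and it stays below 90% until rho is about 0.28.

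**4. The same question without rho.** The SD of benefit may exceed sigma by about 3.5% at 23 per arm, or 8% at 25, before joint power falls below 90%.

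**5. Baseline-adjusted analysis.** Given the unaided score, benefit and aided score have the same residual, so the residual SD can exceed neither the aided-score SD nor the SD of benefit. On the aided-score reading it is sigma × √(1 − rho²), with 2n − 3 df. At 23 per arm, joint power is 0.92, 0.95 and 0.98 at rho 0, 0.3 and 0.5. Simulation with chance baseline imbalance gives 0.915, 0.943 and 0.977. If sigma is the SD of benefit and the unaided score is uncorrelated with benefit, the least favourable case, simulation gives 0.913.

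**6. Limit of step 5.** If sigma is an unaided SD and aided scores vary more, the bound does not protect the 90%. With an aided SD assumed to be 1.1 or 1.2 times sigma, adjusted joint power at rho 0 and 23 per arm is about 85% or 75%.

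**The case against.** The best defence is that there may be no defect at all. All three sigma rows are labelled as benefit, and the row above defines the score difference as benefit minus benefit. On that reading the transfer is valid at 92%. This stands as one of two readings. The footnote supports the other, and the source cited for sigma is not available here to decide between them.

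The 54% figure also needs zero correlation between two completions of the same questionnaire by the same subject about three weeks apart, which is an extreme. That is fair. But the plan gives no correlation, and 0.3 or 0.4 also falls short at either sample size.

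It can further be said that stating the SD would be enough, and that changing the test is a preference. Stating it does close the gap if the t-test is kept. Adjustment is recommended because it secures the power on both readings at almost no cost.

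Four stronger readings are tempting and not supported:
- A reader might infer that 23 per arm is too few. The documents do not show that, because it is enough if sigma is the SD of benefit, or if rho is about 0.46 or more under equal SDs.
- A reader might infer that the plan justifies the transfer by the baseline cancellation. Its stated reason is zero correlation; the cancellation lies behind the SD in the tables.
- A reader might infer that adjustment makes the definition of sigma irrelevant. Step 6 shows otherwise.
- A reader might infer a known rate of needless switching. A simulated 11–12% with no interaction assumes a between-order contrast of 6 against 6 subjects on 10 df. Section 9.4.2.2 words the model differently, with order as a within factor, so the rate is only an illustration. Section 4.2 calls an interaction unlikely.

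**Conclusion.** The point holds as a gap in justification. The paired arithmetic is right, and the cross-over branch and type I error are untouched. In the parallel branch the 90% is unsupported, not shown to be false. Joint power at 23 per arm is 92% if sigma is the SD of benefit. It ranges from 54% to 92% for rho from 0 to 0.5 if sigma is an aided-score SD with an equal unaided SD. These figures rest on a true difference of zero and the plan's product rule. The matter should be fixed because it concerns a prespecified primary analysis. Confidence is medium, since the meaning of sigma cannot be settled from the documents.

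**What to change.** 1. **Section 9.4.2.3.** Replace the unadjusted t-test with one ANCOVA per subscale: benefit (or aided score) on arm and the matching Visit 1 unaided score. Compare the one-sided 95% upper bound of the adjusted HCP-fit-minus-SF benefit difference with the existing margin. With 23 per arm, joint power is then about 91–92% or more, whether sigma is the aided-score SD or the SD of benefit.
2. **Section 9.2.** State which SD sigma is. If it is the aided-score SD, say that carrying 23 per arm over relies on the adjusted analysis. If the t-test is kept, state the assumed SD of benefit and the joint power it gives.

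The cost is SAP wording and one degree of freedom per subscale. The unaided APHAB is already completed by every subject at Visit 1, so no subject, visit or margin changes. The reserve is thin: on the aided-score reading with rho near 0, adjusted joint power is about 90–91% with 22 evaluable subjects per arm and 88–89% with 21.
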